Statistical aspects	
Sample Size Estimation
 
 - The difference between the two groups in changes in PSI-SF scores (primary endpoint) will be expressed in terms of effect size (i.e., the difference in mean scores between groups divided by the common standard deviation at baseline). An effect size of at least 0.5 is widely accepted in the literature as clinically relevant. In a previous study [13], baseline PSI-SF scores were 75.4 ± 2.5, indicating that an effect size of 0.5 corresponds to a between-group difference of 1.25. To detect an effect size of at least 0.5 with 80% statistical power ($\alpha = 0.05$), a minimum of 64 parents per group is required. Assuming a dropout rate of 15%, a total of 150 parents (75 per group) will be enrolled. 
Data Analysis
 
 - Descriptive statistics will be reported as mean and standard deviation or, in the case of non-normally distributed continuous variables, as median and interquartile range. Categorical variables will be reported as percentages. - Between-group comparisons for descriptive variables will be conducted using the Student's t-test or the Mann-Whitney U test for continuous variables, and the chi-square test for categorical variables. - Comparisons between study arms will be performed using Mixed Models for Repeated Measures (MMRM), including the baseline value of the outcome as a linear covariate and study arm as a fixed effect. MMRMs account for both within-subject and between-subject correlations using a first-order autoregressive (AR(1)) variance-covariance structure. Similarly, comparisons between study arms for secondary endpoints, including questionnaire scores and glycemic metrics (change from baseline at 3 and 6 months), will also be conducted using MMRMs. These models will include baseline values of the respective outcomes as linear covariates and the study arm as a fixed effect. Results will be reported as estimated means with corresponding 95% confidence intervals. - Subgroup analyses will also be conducted based on parental sex and child/adolescent age (<10 years vs. ≥ 10 years).
Participating Sites	Participation is planned for six pediatric diabetes centers. Enrollment will be competitive.
Ethics aspects	The study protocol will be submitted for approval to the Ethics Committees of the participating centers.

KEY ROLES AND CONTACTS

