4.3 Procedures for assigning interventions in the study

4.3.1 Randomization procedure

After verification of the eligibility criteria, the parents will be assigned via centralized web-based randomization to participate in either the BEM group activity or the control group (1:1 randomization). In cases where both parents are eligible, they will be allocated to the same study arm. The randomization will be stratified by center.

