7 STATISTICAL CONSIDERATIONS

7.1 Sample Size Calculation

The primary endpoint is the PSI-SF questionnaire score at 3 months after the completion of group activities. The primary efficacy assessment will therefore involve comparing the differences in PSI-SF scores at 3 months relative to baseline between the study arms.

The difference between the two groups in changes of PSI-SF scores will be expressed in terms of effect size (the difference in scores between the two groups divided by the common standard deviation at baseline). It is widely accepted in the literature that an effect size of at least 0.5 can be considered clinically relevant [27]. From the previous study [13], baseline PSI-SF values were 75.4 ± 2.5 ; therefore, an effect size of 0.5 would correspond to a difference of 1.25 between groups.

To detect an effect size of at least 0.5 with a statistical power of 80% ($\alpha=0.05$), at least 64 parents per group need to be evaluated. Assuming a dropout rate of 15%, a total of 150 parents will be enrolled (75 per group)

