7.2 Statistical Analysis

All subjects enrolled in the study will be included in the analysis.

Descriptive data will be expressed as means and standard deviations or as medians and interquartile ranges for continuous variables, and as percentages for categorical variables.

Group comparisons for descriptive variables will be performed using Student's t-test or the Mann-Whitney U test for continuous variables, and the chi-square test for categorical variables.

Regarding the primary endpoint (difference in PSI-SF scores at 3 months compared to baseline), the comparison between study arms will be conducted using mixed-effects models for repeated measures (MMRM), which will include the baseline outcome value as a linear covariate and the study arm as a fixed effect. MMRM accounts for within- and between-subject correlations through a variance-covariance matrix with an autoregressive order 1 structure.

Similarly, comparisons between study arms for secondary endpoints related to questionnaire scores and glucometric measures (differences at 3 and 6 months compared to baseline) will be performed using MMRM.

These models will include the baseline value of the respective outcomes as a linear covariate and the study arm as a fixed effect. Results will be expressed as estimated means with 95% confidence intervals.

In addition to the analysis of the entire sample, subgroup analyses will be conducted separately based on parent sex and children/adolescents' age (<10 years and ≥ 10 years).

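### Subgroup analyses by parent sex and child age are planned separately, with no arm-by-subgroup interaction to judge whether the BEM effect differs

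*Protocol*

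**What the plan says.** Section 7.2 of the protocol first describes the whole-sample analysis. This is a mixed model for repeated measures with the baseline value as a linear covariate and study arm as a fixed effect, reported as estimated means with 95% confidence intervals. It then adds that "subgroup analyses will be conducted separately based on parent sex and children/adolescents' age", with age cut at 10 years. The synopsis (Statistical aspects, Data Analysis) gives the same plan without the word *separately*: "Subgroup analyses will also be conducted based on parental sex and child/adolescent age".

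Neither place names an arm-by-subgroup term or a rule for deciding whether effects differ between levels. The subgroup analyses are not limited to the primary endpoint, and no subgroup proportions are given.

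Two other statements bear on the point. Section 7.1 sizes the trial on the overall comparison: "at least 64 parents per group need to be evaluated" for an effect of 0.5 SD. Section 4.3.1 places two eligible parents of one child in the same arm.

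**The concern.** A subgroup analysis is meant to show whether the arm effect depends on the subgroup factor. That is a question about the difference between two arm differences. Fitting the arm model within each level answers another question, namely whether there is evidence of an effect in that level alone. In a trial sized for 80% power overall, each level is underpowered. One level can easily reach significance while the other does not, even when the true effects are the same. Confidence intervals by level do not remove the problem: an interval that excludes zero beside one that includes it invites the same misreading.

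At stake is a possible claim that BEM helps mothers but not fathers, or parents of younger but not of older children, without a test that supports it. The primary comparison is unaffected.

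**Working it through.** **Inputs from the protocol.** Effect 0.5 SD, power 80%, alpha 0.05 and 64 evaluable parents per arm (section 7.1); allocation "1:1 randomization" (section 4.3.1). The raw scale is not needed, because section 7.1 works in SD units: "baseline PSI-SF values were 75.4 ± 2.5 ; therefore, an effect size of 0.5 would correspond to a difference of 1.25 between groups".

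**Inputs assumed, because the protocol gives none.** The subgroup split, the correlation of baseline with the 3-month score, and the within-couple correlation. The test is taken as two-sided.

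**1. The plan's own figure.** The normal approximation gives 2 × (1.96 + 0.84)² / 0.5² ≈ 62.8, so 63 per arm. The exact noncentral-t calculation gives 64 (power 80.15%; 63 gives 79.52%). The stated 64 is reproduced.

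**2. Power within levels and discordance.** Let p1 and p2 be the power of a two-sample t-test in each level under the same true effect. With independent parents, the chance that exactly one level is significant is p1(1 − p2) + p2(1 − p1). For 0.5 SD, 64 per arm and no gain from baseline adjustment:

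| Split | p1 | p2 | Exactly one significant |
|---|---|---|---|
| 50/50 (32 per arm per level) | 0.504 | 0.504 | 50.0% |
| 60/40 | 0.580 | 0.418 | 51.3% |
| 70/30 | 0.648 | 0.326 | 55.2% |
| 80/20 | 0.707 | 0.229 | 61.3% |

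At the even split this is 2 × 0.504 × 0.496 = 0.50; both levels are significant in 25.4% of cases and neither in 24.6%. If all 75 per arm were evaluable, the range over the same splits is 49% to 63%. In a simulation of 4,000 runs per case, at least one of the two factors was discordant in about 67% to 70% of trials.

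**3. Sensitivity to the assumptions, even split, 64 per arm.**

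- True effect: 9.5% at zero (2 × 0.05 × 0.95), 34% at 0.3 SD, 34% at 0.7 SD, 21% at 0.8 SD.
- Baseline adjustment: a correlation r raises the effective standardised effect to 0.5/√(1 − r²). For r = 0.5, 0.7 and 0.8 this is 0.577, 0.700 and 0.833, and discordance is 47%, 34% and 17%. At 70/30 the figures are 55%, 45% and 30%.
- Couples, for parent sex: if every participant were in a couple with within-couple correlation ρ, and power per level is about 0.5, discordance is 0.5 − arcsin(ρ)/π. That is about 40% for ρ = 0.3 and 33% for ρ = 0.5.

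**4. The interaction test.** With an even split and 64 per arm, each level's arm difference has variance 2/32. The interaction SE is √(2/32 + 2/32) = 0.354 SD. The test declares equal effects different 5% of the time per factor. It has 80% power for a subgroup difference of 2.80 × 0.354 = 0.99 SD. For a difference of 0.5 SD, 0.5/0.354 = 1.41 and 1.41 − 1.96 = −0.55, so power is about 29%.

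**The case against.** The strongest reply is that *separately* is ambiguous. It could mean apart from the whole-sample analysis, or one factor at a time rather than crossed. The synopsis omits the word, and subgroup model terms are often left to a statistical analysis plan, which is not available here. This stands in part: the protocol does not say outright that the arm model is refitted within each level. But section 7.2 contrasts these analyses with that of the entire sample and names only baseline and arm as model terms, so within-level comparison remains the natural reading. On any reading, the protocol gives no method for comparing levels.

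A reader might also infer more than the documents support:

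- *That equal effects would look different about half the time, whatever the truth.* This holds only near a true effect of 0.5 SD and under the assumptions above. The section 7.2 models do adjust for baseline, which lowers the figure at an even split.
- *That the protocol will treat significance in one level only as a differential effect.* No section says so. The objectives and endpoints make no subgroup claim, and results are promised as estimates with confidence intervals.
- *That a finding for mothers and not fathers is likely by chance.* That one direction has probability 0.504 × 0.496 = 25% at the even split; the 50% counts both directions.
- *That couples distort the within-sex results.* A mother and father contribute one parent to each sex-specific analysis, so their correlation does not bias those estimates. It matters when the two sexes are compared, and it makes discordance less likely.

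Finally, the interaction test has little power. That is true, and it is a reason to state its limits in advance.

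**Conclusion.** The concern holds in a limited form. Section 7.2, read naturally, fixes within-level arm comparisons that cannot show whether the BEM effect differs, and it supplies no valid way to judge a difference. At the protocol's design effect and evaluable sample, with independent parents and no gain from baseline adjustment, equal effects would give discordant significance in 50% of trials per factor at an even split, rising to 61% at 80/20. At an even split, changing one assumption at a time over the values examined brings this down to between 9.5% and 47%. Every value computed exceeds the 5% false-difference rate of an interaction test, although the two rates describe different events: the protocol never calls discordant significance a difference. This is an inexpensive improvement to a secondary part of the plan, not a threat to the primary result.

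**What to change.** In section 7.2, and in the synopsis to match, replace the separate subgroup analyses with one full-sample model per factor. It should contain baseline value, arm, subgroup, visit and their interactions, so that the arm-by-subgroup contrast at 3 months can be estimated, and should treat parents of the same family as correlated. Report from that model the arm difference in each level and the interaction estimate, each with a 95% CI. State that a differential effect is judged only on the interaction, and label it exploratory.

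The cost is a sentence or two in the protocol and matching text in the analysis plan, with no new data. The drawback is precision: with an even split, independent parents and no baseline gain, 80% power is reached only for a subgroup difference of about 1.0 SD. The result will usually be inconclusive, and the protocol should say so in advance.

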8 QUALITY ASSURANCE

The study will be conducted in accordance with Good Clinical Practice (GCP) guidelines to ensure the ethics and data integrity of the study. The study documents and data will be stored in the Trial Master File (TMF) and the Investigator Study File (ISF), to be completed and archived in compliance with current regulations.

9 STUDY MONITORING

The investigator/institution will permit monitoring, audits, IRB/IEC review, and regulatory inspections where required, providing direct access to all collected data and original documents. The monitor (CRA) from the Contract Research Organization (CRO) and any potential auditor will have access to all electronic Case Report Forms (eCRFs) and informed consents collected for source data verification. Paper or electronic medical records are considered source documents that provide evidence of the patient's existence and confirm the integrity of the collected data. Source documents are stored at the investigative site.

A monitoring plan will be developed, and monitoring reports will be prepared during various monitoring visits (site initiation visit, remote monitoring, and close-out visit), conducted either remotely or onsite at the investigative centers.

10 ETHICAL ASPECTS

10.1 Ethical Standards

This study will be conducted in accordance with the Declaration of Helsinki concerning medical research involving human subjects (Declaration of Helsinki - Ethical Principles for Medical Research Involving Human Subjects - 64th WMA General Assembly, Fortaleza, Brazil, October 2013), in compliance with the protocol, Good Clinical Practice (GCP), the General Data Protection Regulation (GDPR), and applicable Italian regulations.

The investigator, by signing the protocol, affirms adherence to the instructions and procedures described therein and also declares compliance with GCP principles.

Prior to the initiation of the study, the protocol, the informed consent form, and the information provided to children and their parents must be approved by the local Independent Ethics Committee (IEC). Any amendments to the protocol, except for administrative changes, must also be approved by the local IEC.

10.2 Informed Consent

Before participating in the study, informed consent (IC) must be obtained, signed by each parent, and drafted in accordance with GCP guidelines and national regulatory and legal requirements. The paper IC

must be personally signed and dated by both the parent and the investigator. Any documents related to the parent will be retained by the investigator as part of the study documentation. Each parent will be provided with a signed copy of the informed consent and the clinical trial information sheet. Along with the IC, parents will also sign a authorization for the processing of their personal data and their child's data with DT1.

11 DATA COLLECTION

The medical history and data of children with T1D, who are the offspring of study participants, will be extracted from their medical records and recorded on a pseudonymized eCRF. At study entry, the following information regarding the child will be collected: sex, age, level of education, ethnicity, body weight, height, duration of diabetes, diabetes treatment, presence of diabetes-related complications, last HbA1c value, glucometric data from continuous glucose monitoring (TIR, TAR, TBR), presence of other chronic conditions, hospitalizations in the past year due to severe hypoglycemia, diabetic ketoacidosis, or other reasons, participation in school camps, and engagement in physical activity. The medical records will serve as source documents for these data.

The data required by the protocol will be entered into an electronic case report form (eCRF). The quality and completeness of the data will be verified during and after data collection.

Regarding the parents, the collected data will include age, education level, employment status, marital status (married or cohabiting, separated, divorced, widowed, single/celibate), number of children, household size, and presence of other family members with diabetes. These details will be directly recorded by the parents through personalized access to the dedicated web platform used for the study, which will also facilitate questionnaire completion.

Throughout and at the end of the study, a database review will be performed to monitor data quality and completeness. Any modifications will be tracked using audit trail systems. Once all queries are resolved, the database will be frozen. The database will then be archived and subjected to backup and storage policies in accordance with GCP guidelines, and made available for subsequent audits if required. Raw data will be stored in a database for statistical analysis, which will be conducted after database lock. The impact of missing data on the primary endpoint will be assessed, and the need for imputation techniques will be considered.

An anonymized database will be managed and analyzed at the Center for Outcomes Research and Clinical Epidemiology (CORESEARCH s.r.l.) in Pescara.

12 Publication Policy

All analysis results will be produced solely and exclusively in aggregated form and in a manner that is not attributable, either directly or indirectly, to any individual patient.

The researcher and the sponsor commit to making the results of this study publicly available within one year of its completion, regardless of the outcome. The authorship, acknowledgments, and review procedures for scientific publications will be established prior to the end of the study and before any publication plan is developed.

